6.8.8 Electrocardiograms (ECGs)

A 12-lead ECG will be obtained as per the Schedule of Events and Assessments (Table 2). Additional ECGs may be performed at other times if deemed necessary by the Investigator.

The ECG will be recorded while the subject is resting in a supine position. The ECG will electronically measure the PR, QRS, QT, and QTc intervals, and HR. All ECG tracings will be reviewed within 24 hours by the Investigator or qualified Sub-Investigator. PR intervals will be determined for each of these ECGs from a single reading. Invalid measurements will be repeated. QTc will be reported as QTcF.

7 STATISTICAL METHODS

7.1 General Considerations

All data will be analyzed using SAS® (SAS Institute, Inc., Version 9.3 or later).

In general, continuous variables will be summarized using standard descriptive statistics including number of subjects (n), mean (S), median, interquartile range (Q1, Q3) minimum, and maximum. Categorical variables will be summarized with frequencies and percentages.

The data summaries will be accompanied by individual subject data listings, as specified in Sections 16.2 and 16.4 of ICH Guidance E3, sorted by unique subject identifier. All data available from the electronic CRFs will be listed. Unscheduled measurements will be excluded from the descriptive statistics and statistical analysis but will be included in listings.

Categorical variables will be analyzed using categorical statistical methods such as Pearson's Chi-square test or Fisher's exact test as appropriate.

Treatment comparison for all efficacy variables will be evaluated based on a two-sided significance level of 0.05.

Unless specified otherwise, baseline is defined as the non-missing value collected most recent to and before the time of the very first dose of the SM.

Complete details of the statistical analysis will be provided in a separate SAP.

7.2 Handling of Missing Data

Missing endpoint values in this study may result from subjects discontinuing from the study prematurely or missing intermediate assessments while remaining on study. The primary efficacy analysis method will be based on a Mixed Model for Repeated Measures (MMRM) which utilizes all available data (complete and partial) from subjects included in an analysis set. The MMRM-based approach assumes that missing diary data are MAR. MAR refers to a missingness mechanism that is independent of missing responses, conditionally on observed response history and covariates. That is, given the observed data, the reason for the missing data does not depend on the underlying unseen data.

For primary analysis, missing 28-day MMDs for subjects discontinued due to AE or lack of efficacy will be explicitly imputed by the mean values obtained from MI under the missing not at random (MNAR) assumption before implementing the MMRM. Missing 28-day MMDs for subjects discontinued due to reasons other than AE or lack of efficacy will not be imputed for the primary efficacy analysis.

Sensitivity analyses of the primary endpoint to investigate robustness to missing primary endpoint data will be performed by assuming that missing diary data are MNAR,

meaning that the probability that an observation is missing may depend on its underlying unobserved value. Missing data handling for safety data will be described in the SAP.

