2.2 Secondary Objectives

To assess the efficacy of SPN-538 treatment on the following:

1. Responder rate with a responder defined as a subject with at least a 50% reduction in monthly migraine days (MMDs).
2. Number of days per month requiring acute rescue medication.
3. Monthly rate of total headache days (migraine and non-migraine), duration and severity.
4. Onset of action, defined as the time to first statistically significant treatment effect observed and maintained until the end of study (EOS).
5. Headache Disability Score as measured by the Pediatric Migraine Disability Assessment (PedMIDAS).
6. Health-related quality of life (HRQoL) as measured by the Pediatric Quality of Life Inventory, Version 4.0 (PedsQL 4.0), for the self-report and parent-report.

Primary Estimand

According to the International Conference on Harmonisation (ICH) E9 Addendum, the attributes of the primary estimand (target of estimation) are provided below.

1. Treatment: To compare the treatment effect of SPN-538 vs placebo.
2. Population: The population targeted for the scientific question is defined via the inclusion and exclusion criteria in children 6 to 11 years old (inclusive) with a history of migraine.
3. Variable: The primary efficacy endpoint is the change from baseline in the monthly (28-day) rate of migraine days during the last 4 weeks of the 20-week double-blind Treatment Phase relative to the Prospective Baseline Period based on the Full Analysis Set (FAS) as defined in [Section 7.3](#).
4. Intercurrent event (ICE): For subjects discontinued due to AE or lack of efficacy, missing data will be imputed using MI under the MNAR assumption. For all other missing data due to ICE, missing data will not be imputed following the treatment

[figure not shown]
policy strategy, which assumes that ICE did not occur. Methods of handling missing data are described in [Section 7.2](#).

5. Population level summary: The difference in the mean change from baseline in the monthly (28-day) rate of migraine days during the last 4 weeks of the Treatment Phase between the SPN-538 and placebo groups will be analyzed using a MMRM as discussed in [Section 7.8.1](#).

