7.8.1 Primary Efficacy Analysis

The primary efficacy endpoint, change from the Prospective Baseline Period in 28-day rate MMDs, will be analyzed using MMRM, which assumes that missing data are MAR. All post-baseline study visits will be included in the model; however, the primary comparison will be between SPN-538 and placebo at Month 5 (last 4 weeks of the Maintenance Period). The model will include fixed effect terms for 28-day rate of MMDs for the Prospective Baseline Period, treatment group, Prospective Baseline monthly migraine-specific acute rescue medication (28-day rate) use, visit, and treatment-by-visit interaction as independent variables. The model parameters will be estimated using restricted maximum likelihood method with an unstructured variance-covariance matrix and Kenward-Roger approximation to estimate denominator degrees of freedom.

If the MMRM model with the unstructured variance-covariance matrix does not converge using the default Newton-Raphson fitting algorithm by PROC MIXED in SAS, then the Fisher scoring algorithm or the no-diagonal factor analytic structure will be used (Lu & Mehrotra, 2010). If the model still fails to converge, then the first (co)variance structure which does not have convergence problem will be used for the analysis from the following ordered list:

1. Heterogeneous Toeplitz
2. Heterogeneous Autoregressive of order 1
3. Toeplitz
4. Autoregressive of order 1
5. Compound Symmetry

The denominator degrees of freedom will be estimated using the BETWITHIN option in SAS when any of the covariance structures is used with the sandwich variance estimator.

The least square mean (LS Mean) of each treatment group (placebo and SPN-538) along with the corresponding standard error, p-values, difference in the LS Mean between SPN-538 and placebo (SPN-538 minus placebo), and 95% CIs will be computed at each visit.

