7.8.2 Multiple Comparisons

The overall type I error rate for the study will be preserved at the two-sided 5% significance level by using a sequential (hierarchical) testing for the primary and secondary endpoints. The details will be provided in the SAP

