7.9 Sample Size and Power Considerations

Based on data from previous studies conducted in adolescents and adults (MIGR-001, MIGR-002 and MIGR-003), a common SD of 3 is assumed for both the treatment and control groups. Assuming a treatment difference of 1.1, a sample size of 117 subjects per arm (a total of 234 subjects) will yield 80% power to detect a non-zero difference between the mean change from baseline in the MMDs between the active treatment and the placebo groups using a two-sample t-test at a 2-sided significance level of $\alpha=0.05$.

It is assumed that approximately 15% of subjects will drop-out before completing the study, hence an adjusted total sample size of 276 subjects (138 subjects per arm) will be randomized in a 1:1 ratio to obtain 234 subjects at the completion of the study.

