**Summary of Changes from SAP version 1.0 dated 23 June 2022**

Section, paragraph	Description of Change	Rationale
Cover page	Protocol version and date updated	Per the amended protocol
1	
A sentence is added to clarify that the SAP does not include PK analyses.
 
The sentence “The analysis methods presented in this SAP will supersede the statistical analysis methods described in the clinical protocol” is deleted.
	
Clarification
 
Per FDA

2.2	Items 1 and 4 edited	Per the amended protocol
2.3	Primary Estimand section moved from Section 2.5 to 2.3	Administrative
2.4	Minor edits made to Items 1 and 4, Cognitive assessment added as a safety objective as item 5	Per the amended protocol
2.5	Section Title edited	Per the amended protocol
5.1	Math formula simplified with other minor editions	Administrative
5.2	
Items 1 and 4 re-phrased
 
Math formula simplified with other minor editions
	
Per the amended protocol
 
Administrative

5.3	Minor edit made to item 4	Per the amended protocol
6.2	The last 2 bullet points re-phrased	Per the amended protocol

6.7.1, paragraph 1	The last sentence deleted	Administrative
6.10.1	The last 2 bullet points edited	Per the amended protocol
7.1, paragraphs 1 and 2	Editorial changes	Per the amended protocol
7.3	Editorial change	Per the amended protocol
10	Revised according to the amendment protocol	There is no change in any planned analyses per the amended protocol
11	First reference deleted	Administrative

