### 2.3. Primary Estimand

According to the ICH E9 Addendum, the attributes of the primary estimand (target of estimation) are provided below.

1. Treatment: To compare the treatment effect of SPN-538 vs Placebo.
2. Population: The population targeted for the scientific question is defined via the inclusion and exclusion criteria in children 6 to 11 years old (inclusive) with a history of migraine.

3. Variable: The primary efficacy endpoint is the change from baseline in the monthly (28-day) rate of migraine days during the last 4 weeks of the 20-week double-blind Treatment Phase relative to the Prospective Baseline Period based on the Full Analysis Set (FAS).
4. Intercurrent Events: For subjects discontinued due to adverse event (AE) or lack of efficacy, missing data will be imputed using multiple imputation under the Missing Not at Random (MNAR) assumption. For all other missing data due to Intercurrent events (ICE), missing data will not be imputed following the treatment policy strategy, which assumes that ICE did not occur.
5. Population level summary: The difference in the mean change from baseline in the monthly (28-day) rate of migraine days during the last 4 weeks of the Treatment Phase between the SPN-538 and placebo groups will be analyzed using a Mixed Model for Repeated Measures (MMRM).

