### **10. Changes from Planned Analysis**

There is no change from the planned analyses specified in the protocol.

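### Protocol 7.2 fills adverse-event and lack-of-efficacy dropouts with the mean of the imputations before one MMRM, so as written the primary SE, CI and p-value omit imputation uncertainty

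*Protocol*

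**What the plan says.** Protocol 7.2 sets the order of operations for the primary analysis. Missing 28-day migraine-day values for subjects who discontinued for lack of efficacy or an adverse event "will be explicitly imputed by the mean values obtained from MI under the missing not at random (MNAR) assumption before implementing the MMRM". Values missing for other reasons are left to the model.

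Protocol 7.8.1 then describes one model, fitted by "restricted maximum likelihood method with an unstructured variance-covariance matrix and Kenward-Roger approximation to estimate denominator degrees of freedom", which supplies the LS means, standard errors, p-values and 95% CIs. It mentions no pooling. The same section describes the two sensitivity analyses as run on multiply imputed data; only the primary analysis is given averaged values.

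The estimand text is less specific. The Protocol (Primary Estimand, under 2.2) says "missing data will be imputed using MI under the MNAR assumption", and SAP 2.3 says "missing data will be imputed using multiple imputation under the Missing Not at Random (MNAR) assumption". Neither mentions averaging or pooling.

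Protocol 7.1 refers full details to the SAP. SAP 10 states: "There is no change from the planned analyses specified in the protocol". The SAP's summary of changes records that this sentence was deleted at FDA's request: "The analysis methods presented in this SAP will supersede the statistical analysis methods described in the clinical protocol". SAP 6.7.1 (Missing Efficacy Data) and the body of SAP 7.1 are not in the public copy, so Protocol 7.2 is the only visible text on how the imputations enter the primary test.

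**The concern.** Multiple imputation yields a valid standard error because the analysis is repeated on each completed data set and the spread between the results is added back. Rubin's total variance is T = W + (1 + 1/M)B, with W the average within-imputation variance and B the variance of the estimate between imputations. Averaging the draws first and fitting once loses B. It also shrinks W, because averaging strips most of the residual noise from the filled values. The Kenward-Roger adjustment cannot restore either part, since the model does not know that the values were filled.

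The result affected is the primary comparison at Month 5, from which the testing sequence starts. Protocol 7.8.2 promises that "The overall type I error rate for the study will be preserved at the two-sided 5% significance level".

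**Working it through.** **1. Inputs and the plan's own figure.** Protocol 7.9 gives SD 3, difference 1.1, two-sided alpha 0.05 and 80% power. Then n = 2(1.960 + 0.842)² × 3² / 1.1² = 116.8, so 117 per arm and 234 in total. With 15% dropout, 234/0.85 = 275.3, so 276 randomized (138 per arm). The plan's sample size reproduces and is not in question.

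**2. How many subjects are filled.** Protocol 7.9 says "It is assumed that approximately 15% of subjects will drop-out before completing the study", which is 0.15 × 138 ≈ 21 per arm. Adverse events and lack of efficacy are two of the seven discontinuation reasons in Protocol 3.4.1, and their share is not given. The range used is 7, 14 and 21 imputed per arm (about 5%, 10% and 15%). The top value assumes that every planned dropout is of these two kinds.

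**3. Closed form, within-arm imputation.** Let d be the fraction imputed and R² the share of Month 5 variance that earlier months explain. Both variances are multiples of 2 × 3²/138, whose square root is 0.361.

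- Variance reported by the single fit: proportional to (1 − d) + dR².
- True variance of the estimate: proportional to R² + (1 − R²)/(1 − d).
- At d = 0.15 and R² = 0: reported SE 0.361 × √0.85 = 0.333, true SE 0.361 × √(1/0.85) = 0.392, ratio 0.85. The actual level is 2Φ(−1.96 × 0.85) = 9.6%.
- At d = 0.15 and R² = 0.5: ratio √(0.925/1.088) = 0.922, level 7.1%.
- At d = 0.05: level 6.3% (R² = 0) or 5.6% (R² = 0.5).

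**4. Simulation of the Month 5 contrast.** Assumptions: within-arm imputation without shift, 30 imputations, correlation 0.3 or 0.6, 2,500 runs. The single fill gave type I error of 5.7–6.6% with 7.5% imputed per arm and 7.1–8.4% with 15%. At an assumed 22% active / 8% placebo split it gave 7.7–9.9%. Rubin pooling gave 4.7–6.2%. At 15% and correlation 0.3 the reported SE was 0.337 for the single fill and 0.388 for Rubin.

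**5. Simulation of the MMRM.** Set-up: 138 per arm, baseline plus five months, REML with unstructured covariance, 21 dropouts per arm, 20 imputations, 4,000 runs per case (Monte Carlo SE 0.2–0.5 points). The rescue-use covariate was left out and 270 degrees of freedom replaced Kenward-Roger. Assumptions: correlation 0.6 (autoregressive or exchangeable); dropout spread over the months or early. The within-arm cases in the table add a shift of 1 day.

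| Imputed per arm | Single fill: type I error | Reported SE below true SD | Rubin: type I error |
|---|---|---|---|
| 5% | 6.2–6.9% | 4–5% | 5.0–5.7% |
| 10% | 6.3–8.0% | 7–11% | 4.1–5.1% |
| 15% | 8.0–9.1% | 11–13% | 4.3–4.8% |

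With 5% of placebo and 15% of active subjects imputed within arm and no shift, the single fill gave 6.9–7.2%. The MMRM with no imputation averaged 5.1% over 26 runs, so the excess comes from the fill.

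**6. Same simulation, placebo-based model.** The single fill gave 4.7–5.6% with equal dropout and 3.9–4.3% with the 5%/15% split. Rubin pooling was conservative at 2.3–4.1%. Borrowing the placebo model shrinks the treatment estimate, so its sampling variance falls along with the reported SE.

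**The case against.** The strongest reply is that the operative text cannot be seen. The Protocol defers detail to the SAP, and the two SAP sections that would give it are withheld. A statement of no change from the protocol fits a SAP that adds a pooling step as well as one that does not. The Protocol's change log says 7.2 was revised to align with the SAP, so the SAP may hold the same fill or a fuller procedure. This stands as a limit: nobody can say from the public copy that the SAP omits pooling. It does not rescue the Protocol sentence, which states an order of operations and needs correcting in either case.

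Second, the only imputation model the visible text spells out is placebo-based, for a sensitivity analysis in Protocol 7.8.1. Under that model the single-fill SE is about right. A Month 5 check (1,500 runs, correlation 0.6, all dropouts imputed) put it at 0.98–1.03 of the true SD, and Rubin's SE at 1.12–1.20. This stands too. It is why inflated type I error is claimed only for within-arm imputation and why the fix does not insist on Rubin's rules.

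Third, 15% is an upper bound, and the early-dropout cases stretch their source. The Introduction reports early adverse-event discontinuation on topiramate, whereas the simulation applies it to both arms and to lack of efficacy. That is fair. Without early dropout the within-arm figures are still 6.2–6.3%, 6.3–7.5% and 8.0–8.1%.

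**Conclusion.** The concern holds for the plan as written. The mean of the imputations is a single deterministic fill, and one MMRM on it gives a primary SE, CI and p-value without imputation uncertainty. That much follows from the text of Protocol 7.2 and 7.8.1 and needs no simulation.

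Whether the test also rejects too often is conditional: it does under a within-arm MNAR model and does not under a placebo-based one. The MNAR model, the imputed share, the 1-day shift, the correlations and the dropout timing are all assumptions, so the figures are illustrative. It should be fixed. Confidence is medium, because SAP 6.7.1 and 7.1 cannot be read. If they pool, what is left is a contradiction between Protocol 7.2 and the SAP.

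**What to change.** Replace the sentence in Protocol 7.2 with wording to this effect: *Generate M imputed data sets under the MNAR model specified in the SAP for adverse-event and lack-of-efficacy dropouts, fit the MMRM to each, and combine the Month 5 estimates and standard errors with Rubin's rules or, if the model is reference-based, with a stated variance estimator suited to it.* Confirm that SAP 6.7.1 and 7.1 say the same. The estimand text in both documents is already compatible and needs little or no edit.

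The cost is wording and a few lines of code, with no new data. Under a within-arm model, Rubin pooling raises the reported SE by about 5–6%, 10–12% and 15–17% at 5%, 10% and 15% imputed. Power falls 3–7 points below the single fill (for example, 86.2% to 79.5% at 15%) but stays within 1.5 points of the MMRM without imputation, so what is given up is mostly spurious precision. Under a placebo-based model Rubin pooling would cost 3–9 points of power and be conservative, which is the reason for allowing another variance estimator there.

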7.3 Analysis Populations

The **Randomized Population** consists of all subjects who are randomized via the IWRS.

The **Full Analysis Set (FAS)** is defined as subjects who received at least one dose of study drug and have a baseline and at least one valid post-randomization assessment of monthly migraine based on diary days. The FAS will be used to assess the primary endpoint and secondary efficacy endpoints, and subjects will be included in analyses based on randomized treatment.

The **Per Protocol Set (PPS)** includes all subjects in the FAS who have completed Visits 1-8 with no missing MMDs and no important protocol deviations. PPS will be used as supplementary analysis of the primary and secondary efficacy endpoints with treatment classification based on the treatment received.

The **Safety Analysis Set** includes all subjects randomized into the study who received at least 1 dose of SM. Data will be analyzed according to the treatment received.

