To assess the robustness of the primary analysis under the MAR assumption, two sensitivity analyses will be performed based on multiply imputed data assuming missing data are MNAR. The first sensitivity analysis will be based on placebo-based MI in which missing values for the subjects in the SPN-538 treatment group would adopt the outcome model estimated from the placebo arm. The second sensitivity analysis will be performed using a 'tipping point' methodology to assess the assumption of MAR in the primary analysis. The tipping point analysis will progressively impose increasing shift parameters to the imputed observations under the MNAR assumption in the active treatment arm, not to the placebo arm, to assess how severe departures from MAR must be to overturn the conclusion from the primary analysis.

The details for both approaches will be provided in the SAP.

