### 6.2. Analysis Populations

The following analysis populations are planned for this study:

- **Randomized Population:** All subjects who are randomized via the IWRS.
- **Full Analysis Set (FAS):** Subjects who are randomized, received at least one dose of

study drug and have a baseline and at least one valid post-baseline assessment of monthly migraine based on the headache diary data. The FAS will be used for all efficacy analyses with treatment classification based on the randomized treatment.

- **Per Protocol Analysis Set (PPS):** includes all subjects in the FAS who have completed Visits 1-8 with no missing MMDs and no important protocol deviations. The PPS will be used for supplementary analyses of the primary and secondary efficacy endpoints with treatment classification based on the treatment received.
- **Safety Analysis Set (SAF):** includes all subjects randomized into the study who received at least 1 dose of study medication. Data will be analyzed according to the treatment received. All safety analyses will be conducted using the Safety Population.

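### The compliance denominator ignores dose steps between visits, so adherent subjects can score above 120% in titration; separately, the estimand and the FAS definition need aligning (both minor)

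*Protocol*

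**What the plan says.** **Compliance.** Protocol 7.6 and SAP Section 4 give the same formula. The numerator adds, over Visits 3 to 7, the capsules dispensed less those returned at the next visit. The denominator adds, over the same intervals, the daily capsule number assigned at the opening visit multiplied by the days to the next visit. Both documents (Protocol 7.6, SAP 6.11) use three classes, under 80%, 80-120% and over 120%, with separate summaries for titration, maintenance and the two combined. SAP 6.10.3 lists compliance under 80% or over 120% as a potential important protocol deviation. After review before unblinding, this can remove a subject from the per-protocol set (PPS). It does not say which period's score is meant.

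Protocol 3.1 starts at one 25 mg capsule and adds one every 2 weeks. Table 2 puts Visits 3, 4 and 5 on Days 1, 29 and 57, with telephone contacts on Days 14 and 43.

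**Estimand and analysis set.** The primary estimand in Protocol 2.2 sets the population by eligibility: "The population targeted for the scientific question is defined via the inclusion and exclusion criteria". Its variable is measured "relative to the Prospective Baseline Period based on the Full Analysis Set (FAS) as defined in" Section 7.3. That section limits the FAS to dosed subjects who "have a baseline and at least one valid post-randomization assessment of monthly migraine based on diary days"; SAP 6.2 likewise asks for "at least one valid post-baseline assessment of monthly migraine based on the headache diary data". The intercurrent-event rule in SAP 2.3 reads: "For subjects discontinued due to adverse event (AE) or lack of efficacy, missing data will be imputed using multiple imputation", under a missing-not-at-random (MNAR) assumption. Protocol 7.2 adds that the missing monthly values of these subjects "will be explicitly imputed by the mean values obtained from MI under the missing not at random (MNAR) assumption".

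**The concern.** A compliance score should be 100% when every assigned capsule is taken. Here one capsule count stands for a whole 4-week interval although the assigned dose rises in the middle of it. The denominator is then too small during titration. Adherent subjects look over-compliant, and real under-dosing can pass as acceptable. The planned Titration Period table would be wrong as written, and some under-adherent completers would miss the deviation flag that feeds the PPS.

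The second point is one of wording. Two estimand attributes, the population and the MNAR rule, carry no condition on having data. A third, the variable, is tied to a set that does. A dosed child who stops for an adverse event or lack of efficacy before any valid assessment is covered by the first two and not by the third. The plan should say whether such a child belongs to the primary comparison.

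**Working it through.** **Compliance.** The documents state no expected compliance figure to reproduce; the benchmark is 100% at full adherence.

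Inputs: one capsule added every 2 weeks (Protocol 3.1); at most 4 capsules a day (Protocol 4.3); visits on Days 1, 29, 57, 85, 113 and 141, so five 28-day intervals (Table 2). Assumptions: titration on schedule, with steps after 14, 28 and 42 days; no dose change in maintenance; every capsule taken.

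| Final dose (capsules) | Visit 3-4 | Visit 4-5 | Titration Period | Visits 3-8 |
|---|---|---|---|---|
| 1 | 28/28 = 100% | 28/28 = 100% | 56/56 = 100% | 140/140 = 100% |
| 2 | 42/28 = 150% | 56/56 = 100% | 98/84 = 116.7% | 266/252 = 105.6% |
| 3 | 42/28 = 150% | 84/84 = 100% | 126/112 = 112.5% | 378/364 = 103.8% |
| 4 | 42/28 = 150% | 98/84 = 116.7% | 140/112 = 125% | 476/448 = 106.25% |

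For the 4-capsule row, the numerator in the first interval is 14×1 + 14×2 = 42 and in the second 14×3 + 14×4 = 98. The denominators are 28×1 = 28 and 28×3 = 84. Each maintenance interval adds 28×4 = 112 to both.

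If a subject takes the same fraction of assigned capsules throughout, the displayed score is that fraction times the full-adherence score. At 4 capsules:

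- Titration Period: the 80-120% class holds true adherence from 80/1.25 = 64% to 120/1.25 = 96%.
- Visits 3-8: it holds 80/1.0625 = 75.3% to 120/1.0625 = 112.9%.

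The lower limit over Visits 3-8 is 80/1.0556 = 75.8% at 2 capsules and 80/1.0385 = 77.0% at 3.

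No other single whole capsule count repairs the first interval. Using the end-of-interval dose gives 42/56 = 75%. The rule also errs the other way after a reduction at a telephone contact: 4 to 3 capsules on Day 71 gives (14×4 + 14×3)/(28×4) = 98/112 = 87.5% for that interval at full adherence.

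**Estimand.** No arithmetic applies, because the documents give no count of subjects without a valid assessment. Side by side:

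- Population (Protocol 2.2, SAP 2.3): eligibility only.
- MNAR rule (Protocol 2.2 and 7.2, SAP 2.3): discontinuation for either reason, with no data condition.
- Variable (Protocol 2.2, SAP 2.3): tied to the FAS, which needs a valid assessment after randomization.
- Model (Protocol 7.2): "utilizes all available data (complete and partial) from subjects included in an analysis set".
- Placebo-based sensitivity analysis (Protocol 7.8.1): "missing values for the subjects in the SPN-538 treatment group would adopt the outcome model estimated from the placebo arm". The visible text does not extend this beyond the FAS.

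**The case against.** **On compliance.** The distortion sits mainly in a descriptive table. A subject who leaves at Visit 4 and scores 150% is already outside the PPS, which requires completion of Visits 1 to 8. The flag marks only a potential deviation, and it is reviewed before unblinding. The over-120% class needs a 4-capsule subject titrated on schedule with more than 96% adherence, and Protocol 4.3 allows a dose to be held or reduced. All of this stands and limits the consequence. It does not make the formula right.

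A reader might infer that adherent completers would be dropped from the PPS. The documents do not support that: the Visit 3-8 score of a completer titrated on schedule is at most 106.25%.

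**On the estimand.** A target population and an analysis set may differ, and the attributes can be read together as imputation within the FAS. The SAP sections on missing efficacy data (6.7.1) and the primary analysis (7.1) are listed in its contents, but their text is not visible in the public copy. They may define a valid assessment and the imputation, so nothing can be called missing from them. The rate formula in SAP 5.1 shows no minimum number of diary days, the diary is completed daily (Protocol 6.1), and dosed subjects are to be followed whatever number of doses they took (Protocol 5.1). Few subjects, perhaps none, would lack a valid assessment.

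A reader might infer that the primary analysis drops early adverse-event stops, is biased towards the active arm and loses power. That is not supported. The number is unknown, and the direction would depend on the arm and on how the omitted subjects would have done. What stands is a gap in wording.

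**Conclusion.** The compliance formula is wrong as written. Under on-schedule titration, full adherence scores 112.5% to 125% in the Titration Period at final doses of 2 to 4 capsules, and 100% only at 1 capsule. At 4 capsules an adherent subject is classed above 120%, while 64% true adherence shows as 80%. Over Visits 3 to 8 the inflation is 3.8 to 6.25 percentage points at 2 to 4 capsules, enough for a 4-capsule completer with true adherence between 75.3% and 80% to escape the deviation flag. These figures assume 28-day intervals, no change in maintenance and an even rate of missed capsules. The effect stops at compliance tables, deviation flags and the supplementary PPS; the primary analysis on the FAS does not use the score.

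The mismatch between the estimand and the FAS is real on the visible text, but its size is unknown and possibly nil. No treatment-effect or power figure should be attached to it. Both points are minor.

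**What to change.** 1. **Compliance (Protocol 7.6, SAP Section 4).** Make the denominator the sum, over days, of the capsules assigned on each day, including changes made between visits. A fully adherent subject then scores 100% in every period. State in SAP 6.10.3 that the Visit 3-8 score drives the deviation flag. The cost is wording and programming before database lock, using the record of the dose assigned on each day.
2. **Estimand (Protocol 2.2 and 7.3, SAP 2.3 and 6.2).** Choose one of two routes:
   - Include all randomized, dosed subjects with a baseline, and apply the planned MNAR imputation to adverse-event and lack-of-efficacy stops with no post-baseline value. The downside is that those values rest entirely on the MNAR assumption.
   - Keep the FAS and state its restriction in the estimand, with a pointer to the definition of a valid assessment.

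   Either route is a change of wording; the first also needs programming. Neither change needs new visits or subjects. SAP 6.10.1 already plans FAS and Safety Set counts by arm, so no extra table is required.
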